3.4.3 Exploratory Efficacy Endpoints

Echo measurements of RV size and TAPSE will be summarized using descriptive statistics by visit for each treatment group. A listing of echo variables will be provided.

In addition, individual subject responses in PCWP with exercise will be compared to the select hemodynamic variables and derived indices (at baseline) and echo measurements (at baseline) for correlations to individual subject responses in PCWP (at Week 6) if data permit.

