2 STUDY OVERVIEW

2.1 Study Objectives

2.1.1 *Primary Objectives*

This study will evaluate the efficacy and safety of intermittent (weekly) levosimendan infusions in hemodynamic improvement with exercise in Pulmonary Hypertension with Heart Failure and Preserved Ejection Fraction (PH-HFpEF) subjects.

2.1.2 *Secondary Objectives*

The study will evaluate the effectiveness of intermittent (weekly) levosimendan infusions in improving the following:

- Change in Cardiac Index at rest and with exercise at Week 6
- Change in pulmonary vascular resistance (PVR) effect at rest and with exercise at Week 6
- Change in pulmonary capillary wedge pressure (PCWP) when supine and legs elevated at Week 6
- Patient global assessment (based on a six-point Likert scale) at Week 6
- Exercise duration 6-min walk test at Week 6
- Physician's Assessment of Functional Class
- Clinical Events: Death and hospitalizations
 - All cause hospitalizations
 - Hospitalizations attributed to any abnormality in cardiac and/or pulmonary status.

2.1.3 *Exploratory Objectives*

Baseline echocardiographic measurements of right ventricle (RV) and left ventricle (LV) function to predict favorable response to levosimendan therapy.

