2.2 Study Design

2.2.1 *Overview*

[figure not shown]
This study will be conducted at approximately 20-25 sites in the United States. The Phase 2 study of levosimendan in PH-HFpEF subjects has been designed in two phases (Figure 1). The study will recruit male and female subjects meeting identified enrollment criteria for PH-HFpEF into the lead-in open label phase to identify “responders” to levosimendan intravenous infusion of at 0.10 µg/kg/min for 24 hours \pm 30 min. Subjects that have clinically relevant responses to levosimendan will be randomized to levosimendan or placebo (1:1) and receive intermittent (weekly) study drug infusions (Week 2-5). The first 36 subjects who demonstrate a \geq 4mmHg reduction in PCWP from baseline measured at bicycle exercise (25 watts) with no more than a 10% decrease from baseline in cardiac index will be classified as a “responder” to the

lead-in levosimendan dose and be randomized to the double-blind phase of the study. Patients who do not tolerate the initial levosimendan infusion due to excessive hypotension or tachycardia will be dropped from eligibility. In the double-blinded phase, patients will be randomized to levosimendan or placebo and receive a weekly dose of study drug intravenously at $0.075 \mu\text{g}/\text{kg}/\text{min}$ for 24 hours ± 30 min and if tolerated titrated to $0.10 \mu\text{g}/\text{kg}/\text{min}$ for 24 hours ± 30 min at Week 4. The infusion rate of study drug may be decreased or interrupted as clinically warranted if the subject has hypotension, tachycardia, or signs or symptoms consistent with hypovolemia (e.g., low systolic blood pressure [SBP], decreasing urine output with rising blood urea nitrogen [BUN] and serum creatinine) Record the time of discontinuation or down titration. Patients should be monitored closely until clinically stable. See Protocol Attachment 1 for infusion rates and instructions on dose adjustments. Patients will be evaluated Week 6 to determine the efficacy and safety of levosimendan. Randomized subjects that have not received study drug weekly through Week 5 and returned for evaluation on Week 6 will be replaced to ensure 18 subjects have completed in each study group.

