3.3.3 Demographic and Baseline Characteristics

The following demographic and baseline characteristics will be summarized:

- Age (years) and age categories (<65 years, ≥65 years)
- Sex
- Race
- Ethnicity
- Height (cm)
- Weight (kg)
- Body mass index (BMI) (kg/m²)
- Baseline hemodynamic parameters (PCWP, Cardiac Index, PVR, PAP (mean), RAP)
- Baseline echo measurements
- Baseline 6-Minute Walk Test (exercise distance) (m)

Demographic and baseline characteristics will be summarized with descriptive statistics or counts and percentages of subjects as appropriate by treatment assignments in the double-blind phase and in total for the Safety Analysis Set and Full Analysis Set.

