3.4.1 Primary Efficacy Endpoints

Primary Analysis

The primary efficacy variable is defined as the change from baseline PCWP with bicycle exercise (25 watts) at 6 weeks. The baseline PCWP with bicycle exercise (25 watts) is defined as the value obtained prior to lead-in study drug infusion at Visit 1.

The primary efficacy analysis will be conducted over the Full Analysis Set. The PCWP will be analyzed using an analysis of variance (ANOVA) model with change from baseline to Week 6 in PCWP as dependent variable, treatment group as a factor.

An example of SAS code is provided below:

```
*****

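### The planned correlations of baseline variables with PCWP response include no treatment contrast, so they cannot separate predictors of response to levosimendan from prognostic markers.

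*SAP*

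**What the plan says.** Section 2.1.3 (Exploratory Objectives) gives the purpose: baseline measurements of RV and LV "function to predict favorable response to levosimendan therapy".

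Section 3.4.3 (Exploratory Efficacy Endpoints) gives the only analysis aimed at that purpose. Selected hemodynamic variables, indices derived from them and echo findings, all taken at baseline, are to be examined "for correlations to individual subject responses in PCWP (at Week 6) if data permit". It does not name the selected variables, define response, give a correlation method, or say whether the arms are pooled. It states no comparison between arms and no adjustment for baseline PCWP.

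Other sections bear on how this is read:

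- Section 3.4.1: "The primary efficacy variable is defined as the change from baseline PCWP with bicycle exercise (25 watts) at 6 weeks", with the baseline value "defined as the value obtained prior to lead-in study drug infusion at Visit 1".
- Section 2.2.1: a lead-in responder is identified by a "reduction in PCWP from baseline measured at bicycle exercise (25 watts") of at least 4 mmHg, with a limit on the fall in cardiac index.
- Section 3.3.3: the baseline characteristics to be summarized include "Baseline hemodynamic parameters (PCWP, Cardiac Index, PVR, PAP (mean), RAP").
- Section 3.4: efficacy analyses are performed by assigned treatment in the double-blind phase.

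**The concern.** Predicting response to a drug is a question about effect modification: does the levosimendan-minus-placebo difference vary with the baseline marker? The change in one subject combines drug effect, natural course, regression to the mean and measurement error. A marker that tracks this change equally in both arms is prognostic and says nothing about who benefits from levosimendan, yet it would show up as a correlation. The trial has a randomized placebo arm that can separate the two, and section 3.4.3 does not plan to use it for this. This part holds for every predictor, including the echo measurements named in the objective.

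A second problem is conditional. If response means change from baseline, and baseline exercise PCWP is one of the selected variables, then baseline sits on both sides of the correlation. A negative association then appears by construction.

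At stake is the reading of the exploratory results: a correlation could be reported as identifying levosimendan responders when it shows nothing of the kind.

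**Working it through.** **The plan's own figure.** The SAP gives no figure for the predictor analysis. The simulations below take their inputs from section 2.2.3: 36 subjects allocated 1:1 (18 per arm), SD 5 mmHg, difference 4.9 mmHg, two-sided 0.05, stated power 80%. A two-sample t test with 18 per arm gives 81.5% (17 per arm: 79.1%), so the stated power reproduces. The SAP does not say whether the SD is of the change; it is taken as such here.

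**Step 1: prognostic-only marker.** Assume a marker has the same correlation r with the change in PCWP in both arms, so that it does not modify the drug effect. Over 5,000 simulated trials, the share with p<0.05 was:

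| r | Correlation, levosimendan arm (n=18) | Correlation, pooled (n=36) | Treatment-by-marker interaction |
|---|---|---|---|
| 0.3 | 23% | 36% | 4.3% |
| 0.5 | 58% | 81% | 5.3% |

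The correlation detects the marker's prognostic relation. Only the interaction test keeps about its nominal 5% for the question the objective asks.

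**Step 2: built-in correlation, if response is change and baseline exercise PCWP is a predictor.** Let X be baseline, Y the Week 6 value, with equal variances, correlation rho and no drug effect. Then Cov(X, Y−X) = (rho−1)·σ² and Var(Y−X) = 2(1−rho)·σ², so

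corr(X, Y−X) = −(1−rho)/√(2(1−rho)) = −√((1−rho)/2).

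The SAP does not give rho; a range is assumed. The p-value is for a sample correlation equal to this value, from t = r·√((n−2)/(1−r²)) on n−2 degrees of freedom:

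| Assumed rho | Built-in r | p, n=18 (one arm) | p, n=36 (pooled) |
|---|---|---|---|
| 0.3 | −0.59 | 0.01 | 0.0001 |
| 0.5 | −0.50 | 0.035 | 0.002 |
| 0.7 | −0.39 | 0.11 | 0.02 |
| 0.9 | −0.22 | 0.37 | 0.19 |

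For example, at rho 0.5 and n=36, t = −0.50·√(34/0.75) = −3.37 and p = 0.002. In 20,000 simulated trials per rho with no drug effect, the share with p<0.05 at n=18 / n=36 was 59% / 89% at rho 0.5, 36% / 66% at 0.7, and 14% / 26% at 0.9.

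**Step 3: pooling with a real drug effect.** A 4.9 mmHg difference between equal arms adds (4.9/2)² = 6.0 to a within-arm variance of 25. The correlation shrinks by √(25/31.0) = 0.90, so the first three values become about −0.53, −0.45 and −0.35. The artifact is diluted but remains.

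**Step 4: what the interaction test can deliver.** With 36 subjects, simulated power is about 28% if the drug effect changes by 2.5 mmHg per SD of the marker, and about 75% if it changes by 4.9 mmHg per SD.

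**The case against.** The strongest reply is that section 3.4.3 describes an exploratory look, conditional on the data, with no test or decision rule, and that the interaction model would itself often leave the question open at this sample size. The low power is real. But exploratory status excuses imprecision, not a method aimed at a different question: a wide interval around the right quantity is more useful than a tighter estimate of the wrong one.

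It can also be said that section 3.4 puts efficacy analyses on assigned treatment, so the correlations might be run by arm. That reading is open, but two separate correlations do not test whether they differ.

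Several objections stand and limit the point:

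- Section 3.4.3 does not use the word change. Sections 3.4.1 and 2.2.1 make it the likely reading, but it is an inference.
- Baseline PCWP is not named as a predictor. Section 3.3.3 lists it as a characteristic to summarize, and the objective names only echo measurements. If it is not selected, the built-in correlation lapses for it; the missing treatment contrast does not.
- A reader might infer that the built-in correlation will always be significant. It depends on rho and on pooling: one arm at rho 0.7, or either sample size at rho 0.9, gives p above 0.05.
- A reader might infer that every index calculated from PCWP shares the negative sign. The SAP gives no formulas. If PVR is calculated by subtracting PCWP, measurement error would push the other way.
- A reader might infer that a spurious predictor will enter later selection criteria. Nothing in the SAP links this analysis to such a decision.

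**Conclusion.** The point holds as a mismatch between objective and method. Section 2.1.3 asks who responds to levosimendan; section 3.4.3 plans correlations that cannot distinguish prognosis from modification of the drug effect, whether pooled or within an arm. Under the assumed prognostic correlations of 0.3 and 0.5, a marker with no bearing on the drug effect would look significant in 23% to 81% of analyses, against about 5% for an interaction test.

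The built-in negative correlation is conditional on two readings that the SAP suggests but does not state, and its size rests on an assumed rho and equal variances. It is substantial at rho 0.3 to 0.7 and modest at 0.9.

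The correlations remain usable as description; what they do not support is a claim about response to levosimendan. The matter is minor: it concerns an exploratory aim only, and the primary analysis is untouched.

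**What to change.** In section 3.4.3, name the baseline predictors and define the response. For each echo or hemodynamic predictor, fit the change in exercise PCWP (or the Week 6 value) on treatment, baseline exercise PCWP, predictor and treatment-by-predictor interaction. When the predictor is baseline exercise PCWP itself, fit only treatment, baseline PCWP and their interaction; otherwise the same covariate enters twice and the model is not estimable. Report the interaction estimate with its 95% confidence interval, show scatter plots by arm, and label the results hypothesis-generating.

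The cost is a little programming: Sensitivity Analysis 1 in section 3.4.1 already fits treatment and baseline, so only the marker and its interaction are added. The downside is wide intervals with 36 subjects, which the report should state.

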3.5 Pharmacokinetic Assessment

The Pharmacokinetic (PK) analyses will be documented in a separate file and performed by another vendor and reported separately.

3.6 Safety Assessment

Safety data will be summarized by actual treatment received (and in total for selected analyses) in the double-blind phase based on the Safety Analysis Set.

3.6.1 Adverse Events

An AE is any untoward medical occurrence in a clinical investigation subject administered a pharmaceutical product and that does not necessarily have a causal relationship with this treatment. All AEs are collected from the time the informed consent is signed until the subject discontinues or until Week 6 (whichever is first). All AEs will be coded to system organ class and preferred term using MedDRA version 21.0. Treatment-emergent adverse events (TEAEs) are defined as AEs that start after the first dose of study drug (lead-in infusion).

TEAEs with onset during the lead-in phase and double-blind phase will be summarized separately. TEAEs that start on or after the lead-in infusion and prior to the first double-blind infusion will be attributed to the lead-in phase, while TEAEs that start on or after the first double-blind infusion will be attributed to the double-blind phase. All AEs that start prior to the lead-in infusion will be listed.

Adverse events of special interest include the following preferred terms: hypotension, atrial fibrillation, clinically significant arrhythmia, aborted resuscitated death, and stroke.

An overview of TEAEs will be provided including counts and percentages of subjects with the following:

- Any TEAEs (overall and by maximum severity)
- Any study drug related TEAEs (overall and by maximum severity)
- Any TEAEs of special interest (overall and by maximum severity)
- Any serious TEAEs (TESAEs)
- Any TEAEs leading to discontinuation of study drug
- Any TEAEs leading to discontinuation of study
- Any TEAEs leading to death

Counts and percentages of subjects will also be presented by system organ class and preferred term for each of the categories in the overview.

Listings will be presented specifically for SAEs and TEAEs leading to discontinuation of study drug.

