If a subject terminates the study prematurely, procedures listed in the Week 6 visit should be performed as soon as possible. The RHC, echocardiogram, and 6-minute walk test (6MWT) do not need to be performed for subjects who terminate the study early. Subjects will be followed for safety for 2 weeks after early termination. A phone contact will be made with the subject at 24 hours (+ 24 hours), 7 days (+ 2 days), and 14 days (+ 2 days) post infusion by investigational site personnel to assess any new or ongoing adverse events. If a subject discontinues greater than 24 hours after their prior infusion, the 24-hour phone contact does not need to be performed and the next phone contact beginning at 7 days should be completed. The vital status of all subjects will be collected at the end of the trial, regardless of reason for discontinuation.

Refer to Protocol for the time and events schedule of the study procedures.

Figure 1: Study Design Flow Chart

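### SAP Section 3.6.1 ends adverse event collection at discontinuation, while Section 2.2.1 plans later calls to look for adverse events; the two rules need reconciling.

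*SAP*

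**What the plan says.** Section 3.6.1 (Adverse Events) sets the collection period, which runs from consent "until the subject discontinues or until Week 6 (whichever is first". It then defines a treatment-emergent AE (TEAE) by its start relative to the lead-in infusion. Each TEAE goes to the lead-in or the double-blind phase according to whether it began before the first double-blind infusion. Neither of these counting rules has an end date.

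Section 2.2.1 (Overview, under 2.2 Study Design) describes what happens after early termination: "Subjects will be followed for safety for 2 weeks after early termination". Site staff phone the subject "at 24 hours (+ 24 hours), 7 days (+ 2 days), and 14 days (+ 2 days) post infusion", and the purpose of the calls is "to assess any new or ongoing adverse events". The same paragraph adds "If a subject discontinues greater than 24 hours after their prior infusion, the 24-hour phone contact does not need to be performed", and closes with "The vital status of all subjects will be collected at the end of the trial, regardless of reason for discontinuation".

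Section 5, which lists departures from the protocol, does not mention the AE collection period.

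**The concern.** One section closes AE collection on the day a subject discontinues. Another schedules contact after that day in order to find AEs. An event that first appears between discontinuation and the last call is inside one rule and outside the other.

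The subjects affected appear in few other places. The Full Analysis Set (3.2.5) requires the Week 6 visit, and subjects who stop before it are replaced (3.3.1), so early terminators drop out of the efficacy comparison. The Safety Analysis Set (3.2.4) keeps them, and its tables are where their experience is meant to be reported. If the collection sentence in 3.6.1 is applied as written, non-fatal TEAEs, serious events and special-interest events from the post-termination period can be left out. If sites record the events but the sentence is read in different ways, two programmers could build different tables from the same data.

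**Working it through.** **Step 1. Can one reading satisfy both sections?** The conflict would vanish if discontinuation in 3.6.1 meant the end of the two-week follow-up. Section 2.2.1 does not use the word that way. Its rule for skipping the 24-hour call ("If a subject discontinues greater than 24 hours after their prior infusion, the 24-hour phone contact does not need to be performed") treats discontinuation as an event that comes before the calls. The SAP gives the word no second meaning, so the calls lie after the point at which 3.6.1 stops.

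**Step 2. How much follow-up lies outside the period?** Inputs: nominal infusion days 1, 8, 15, 22 and 29, and Week 6 at Day 36, all from the visit windows in 3.1.3; contact offsets of 1, 7 and 14 days, with +2 days on the last, from 2.2.1. Formula: contact day = last infusion day + offset.

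| Last infusion (day) | 24-hour call | 7-day call | 14-day call | Latest 14-day call (+2) | 14-day call past Day 36? |
|---|---|---|---|---|---|
| 1 | 2 | 8 | 15 | 17 | No |
| 8 | 9 | 15 | 22 | 24 | No |
| 15 | 16 | 22 | 29 | 31 | No |
| 22 | 23 | 29 | 36 | 38 | Only by using the window |
| 29 | 30 | 36 | 43 | 45 | Yes |

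For a subject who stops on an infusion day, all the calls fall after discontinuation, so up to 14 days (14 + 2 = 16 with the window) are outside the 3.6.1 period. This is a maximum, because the calls are timed from the infusion and not from termination. For example, a subject who stops 6 days after an infusion has 14 − 6 = 8 days left to the nominal last call. The table counts from the nominal infusion day; if the clock starts at the end of the 24-hour infusion, each contact moves one day later.

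**Step 3. Is the discontinuation limb the only problem?** No. After a Day 29 infusion the 14-day call falls on Day 43, which is 43 − 36 = 7 days past nominal Week 6. Deleting the words about discontinuation would still leave that call outside the period.

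**Step 4. What happens to an event that is recorded anyway?** The TEAE definition and the phase rule have no end date, and Section 6 lists all available data. A late event that reaches the database could therefore be counted and would be listed. The risk is that the event is not recorded because 3.6.1 says collection has ended, or that it is recorded and then treated as out of period.

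**Step 5. What follow-up would completers have?** From the Day 29 infusion to Day 36 is 36 − 29 = 7 days, against up to 14 days for an early terminator.

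**The case against.** The best reply is that the 3.6.1 sentence describes collection and drops nothing from the analysis. The calls are required, their purpose is to find AEs, and the counting rules are open-ended, so a recorded event would be counted. This stands in part. It means loss is possible, not certain. It does not remove the contradiction, because the sentence that defines what is collected still stops too early.

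Four stronger conclusions are tempting, and the SAP does not support them.

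- **A reader might infer that AE counts are biased downward.** That follows only if sites stop recording, or analysts exclude, what the calls find. The SAP does not say that either will happen.
- **A reader might infer bias between the arms.** The SAP gives no dropout rates by arm. Subjects who cannot tolerate the lead-in because of hypotension or tachycardia leave before randomization and belong to no arm. That early terminators are those most likely to be harmed is a plausible inference, not something the SAP states.
- **A reader might infer that deaths are missed.** Vital status is collected for every subject at the end of the trial, and 3.4.2 plans a by-subject listing of deaths from any cause. What remains open is narrower: whether a fatal AE with late onset enters the row for TEAEs leading to death.
- **A reader might size the problem as one event in 18, or 5.6 percentage points.** Eighteen per arm is the number of completers after replacement. An early terminator is additional to them, so once replacement is complete an arm with one has at least 19 randomized subjects (1/19 = 5.3 points if all were dosed). The Safety Analysis Set also includes subjects given only the open-label infusion. No single percentage fits.

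**Conclusion.** The two sections contradict each other and nothing else in the SAP reconciles them. This is not a detail left to the protocol, since the SAP states both rules itself.

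The size can be stated only as time: up to 14 days after the last infusion (16 with the window) for an early terminator, running past nominal Week 6 after a Day 29 infusion. Within that time, non-fatal TEAEs, serious events and special-interest events can be lost or handled inconsistently. The number of events cannot be estimated from the SAP.

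The conclusion rests on the literal wording of 3.6.1, on discontinuation having the same meaning in both sections, and on nominal visit days. It is worth correcting because these are safety data that the study already plans to seek.

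**What to change.** Reconcile the two sections before database lock. Section 3.6.1 should say that AEs are collected and tabulated from consent to Week 6 for subjects who complete, and through the last safety contact planned in 2.2.1 for subjects who terminate early. The existing phase rule in 3.6.1 can assign these events unchanged. Name the last contact as the end point, because 2.2.1 counts the two weeks from termination but times the calls from the infusion.

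The cost is about one sentence, with no new visits or calls. The SAP does not show whether the eCRF already accepts AEs dated after discontinuation; if it does not, that entry must be enabled.

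There is a small downside to state in the SAP: early terminators would be observed for up to 14 days after the last infusion and completers for about 7. A table footnote giving the two periods would let a reader allow for this.

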3 STATISTICAL METHODOLOGY

3.1 General Considerations

3.1.1 *Study Day*

Study day will be calculated from the date of first dose of study drug (lead-in infusion). The day of the first dose of study drug will be Day 1, and the day immediately before Day 1 will be Day -1. There will be no Day 0.

3.1.2 *Definition of Baseline*

Baseline is defined as the value obtained prior to lead-in study drug infusion on Visit 1. Note: The protocol-specified visit ‘Day 0’ will be referred to as ‘Visit 1’ for analysis purposes.

3.1.3 *Analysis Visit Windows*

Post-baseline assessments will be assigned a visit number based on the study day. Analysis visit windows will be defined as below:

- Screening: ≤ 28 Days Prior to Visit 1,
- Lead-In Visit: Visit 1/Week 1/Day 1,
- Visit 2/Week 2/Day 8: Day 2 to Day 11,
- Visit 3/Week 3/Day 15: Day 12 to Day 18,
- Interim Office Visit: Between Visit 3/Week 3 and Visit 4/Week 4,
- Visit 4/Week 4/Day 22: Day 19 to Day 25,
- Visit 5/Week 5/Day 29: Day 26 to Day 32, and
- Visit 6/Week 6/Day 36: Day 33 or later.

3.1.4 *Summary Statistics*

Categorical data will generally be summarized with counts and percentages of subjects. The denominator used for the percentage calculation will be clearly defined. Continuous data will generally be summarized with descriptive statistics including n (number of non-missing values), mean, median, standard deviation, minimum, and maximum.

3.1.5 *Handling of Dropouts and Missing Data*

In cases of missing or incomplete data (e.g. adverse event [AE] and concomitant medications), the missing component(s) will be assumed as the most conservative value possible. For example, AEs with missing start dates, but with stop dates either overlapping into the treatment period or missing, will be counted as treatment-emergent, taking the worst-case approach. When partial dates are present in the data, both a partial start date and/or a partial stop date will be evaluated to determine whether it can be conclusively established that the AE started prior to the start of study drug or ended prior to the start of study drug. If the above cannot be conclusively established based on the partial and/or present dates, then the AE will be considered as treatment-emergent. Actual data values as they appear in the original eCRF will be presented in the data listings. Missing values for other variables will not be imputed and only observed values will be used in data analyses and presentation.

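### TEAEs and their study phase are assigned by onset alone, so the double-blind summary can miss events that began earlier and worsened on blinded drug

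*SAP*

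**What the plan says.** Section 3.6.1 of the SAP collects adverse events from consent and gives four rules, all based on when the event started.

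- Treatment-emergence: "Treatment-emergent adverse events (TEAEs) are defined as AEs that start after the first dose of study drug (lead-in infusion".
- Lead-in phase: "TEAEs that start on or after the lead-in infusion and prior to the first double-blind infusion will be attributed to the lead-in phase".
- Double-blind phase: "TEAEs that start on or after the first double-blind infusion will be attributed to the double-blind phase".
- Before the lead-in: "All AEs that start prior to the lead-in infusion will be listed".

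The tables follow these rules: "TEAEs with onset during the lead-in phase and double-blind phase will be summarized separately". The overview begins with "Any TEAEs (overall and by maximum severity"). Its other rows (drug-related, special interest, serious, leading to discontinuation, leading to death) are also subsets of TEAEs. Section 3.6 groups safety data by the treatment actually received in the double-blind phase. For partial dates, section 3.1.5 looks at the dates to "determine whether it can be conclusively established that the AE started prior to the start of study drug" or ended before then. If neither can be shown, "then the AE will be considered as treatment-emergent".

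**The concern.** The double-blind TEAE summary is the only by-arm adverse event comparison confined to the randomized period. By then every subject has received a 24-hour open-label infusion of levosimendan (section 2.2.1). Intolerant subjects are dropped, but subjects with milder, tolerated events can go on to randomization. The same section foresees hypotension and tachycardia during study drug infusions, and section 3.6.1 names hypotension and atrial fibrillation as events of special interest. So an event of this kind could begin in the lead-in and be made worse by repeat levosimendan but not by placebo.

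Because every overview row is a subset of TEAEs, onset decides more than the severity grade. It also decides in which phase a serious event, a discontinuation or a death is shown.

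**Working it through.** The SAP states no figure on this point, so the check traces event histories through the rules. Assume first that a change in severity stays on the same adverse event record.

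1. **Onset before the lead-in, worsening on blinded drug.** The event did not start after the first dose, so it is not a TEAE. It goes to the pre-lead-in listing and enters no TEAE table in either phase.
2. **Onset in the lead-in, worsening or becoming serious on blinded drug.** It is a TEAE of the lead-in phase. Its maximum severity and seriousness are shown in the lead-in summary, and the double-blind summary does not contain it.
3. **Onset in the double-blind phase, then worsening.** It is a double-blind TEAE and is counted at maximum severity. Nothing is lost.

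Now assume instead that sites open a new record on worsening. The new record in cases 1 and 2 has its own start within the double-blind phase and is counted there. The gap closes.

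The result therefore depends on a recording convention that this SAP does not state and does not refer to.

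**Check of the anchor.** The definition uses a start after the first dose, while the phase rule uses a start on or after the lead-in infusion. Inputs: infusion of 24 hours (section 2.2.1); nominal interval from Day 1 to Day 8 (section 3.1.3), which is 7 × 24 = 168 hours.

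- If the dose is counted from the start of the infusion, only an onset at the exact start time is in doubt.
- If it were counted from the end, onsets during the infusion would be neither TEAEs nor pre-infusion listed events. That window is 24/168 = 14.3% of the nominal interval. This is a share of time, not of events.

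Section 3.1.5 refers to the start of study drug, and the pre-treatment listing takes only events that begin before the infusion. Both point to the start.

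**The case against.** The strongest objection is that the handling of worsening is a data-recording rule, which commonly sits in the protocol or the eCRF guide. Neither is shown. If a worsening opens a new record, the existing rule captures it. This stands, and it makes the point conditional. It does not remove it, because the analysis definition should give the right table without relying on an unstated convention.

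Second, lead-in-onset events are not erased. Given the grouping in section 3.6, they would appear by arm, at maximum severity, in the lead-in summary. This also stands: for these events the fault is placement. A reader of that table would, however, take the severe grade as an effect of the open-label infusion. Events with onset before the lead-in do drop out of all TEAE tables.

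Third, there are other views of the data: a listing of serious events, vital signs by visit and arm, cardiac-monitoring shifts to Week 5, and deaths and hospitalizations compared by arm. These help in part. Listings do not compare arms. The comparison of deaths and hospitalizations uses the Full Analysis Set, which requires completion of the Week 6 visit.

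Two stronger readings are tempting but unsupported.

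- A reader might infer that the two anchors are incompatible rules that lose infusion-day events. The surrounding text points to the start of infusion, so this is loose wording.
- A reader might infer that partial dates leave phase with no governing principle. Section 3.1.5 opens with a general most-conservative rule and gives treatment-emergence as an example, although it does not spell out phase. Defaulting such events to the double-blind phase could also move open-label levosimendan events into the placebo arm, so no such default is proposed.

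**Conclusion.** The point holds in a conditional form. As written, treatment-emergence and phase rest on onset alone. If worsening is kept on the original record, the double-blind by-arm TEAE summary omits events that began earlier and were aggravated on blinded drug.

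It would be too strong to say that a worsening event is never counted against blinded drug. Events that start in the double-blind phase are counted there at maximum severity, and a newly recorded worsening would be too.

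No size can be given. The documents contain no rate of lead-in events, of their persistence or of their worsening, and any example count would be invented. The direction is clear under one assumption: if repeat levosimendan aggravates earlier events more than placebo does, the double-blind summary understates the difference between arms. The difference in anchor wording is minor and needs only tidying.

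**What to change.** In section 3.6.1:

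- Define a TEAE as an adverse event that starts, or worsens in severity or seriousness, at or after the start date and time of the lead-in infusion.
- Keep phase attribution by onset, and count also in the double-blind phase any event that worsens at or after the start of the first double-blind infusion.
- Use the start of the infusion as the single anchor in every sentence that now refers to the first dose or to the infusion.

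The cost is SAP wording and table programming, and section 1 leaves room for this because the SAP is to be finalized before database lock. There are two downsides. The rule needs the date of the severity change, so it works only where that date is recorded. An event may also appear in both phase tables, which a table footnote should say.
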